The proposed study will use parallel-groups, randomized, sham controlled, double-blinded design in which 36 participants with motor incomplete SCI (AIS B – D level) will randomly assigned to receive tDCS combined with repetitive arm training (RAT) or sham tDCS combined with R-A training. During the first 20-minute participants (n=24) in the experimental group will receive 20 minutes of anodal tDCS (2 mA) on motor cortex contralateral to their trained side followed by RAT for 60 minutes. Participants (n=12) in the control group will receive 20 minutes of sham tDCS followed by RAT for 60 minutes. In the sham stimulation 2 mA of anodal current will be delivered in a ramp up and down fashion for 30 seconds at the beginning and 30 seconds at the end of 20 minutes of stimulation. Treatment will be administered at an intensity of 5 sessions per week for 2 weeks.

The randomization schedule will be provided by project statistician ([name]).

Outcome measure:

Feasibility outcome measure: Adherence with therapy will be measured as;
(1) the number of treatment sessions attended by each participant,
(2) number of drop-outs in each group,
(3) participant's perceptions of the use of study implementation (using the tDCS and exercise equipment, numerical rating scale with 'not difficult at all' at 0, and 'very difficult' at 10)
(4) participant's perceptions of usefulness of the intervention (numerical rating scale with 'not at all useful' at 0 and 'very useful' at 10).

The telerehabilitation intervention will be considered as feasible if at least 80% adherence rate is achieved (completed number of sessions \geq 8 out of 10), if attrition rate is no higher than 10% in each study group, if at least 40 minutes of 60 minutes exercise session is completed and if no serious adverse events took place (other than expected side effects from tDCS).

Clinical outcome measure: Primary clinical outcome measure is GRASSP prehension performance (Kalsi-Ryan et al., 2012). Secondary clinical outcome measures are grip strength and Spinal Cord Injury Independence Measure (SCIM III) (Itzkovich, Gelernter et al. 2007). Assessments will be repeated immediately after completion of 10 sessions and at 4-weeks follow-up.

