Schedule of activities

Event	Baseline (Day -6 to 0)	Treatment Sessions (1-10)	Post-treatment (Day 5±3)	Follow-up 1 (Day 35±5)
Informed Consent	X			
Inclusion/Exclusion Criteria	X			
Demographics	X			
Medical and Social History	X			
Medication Checklist	X		X	X
ASIA-Impairment Scale	X		X	X
GRASSP	X		X	X
Grip Strength				
NHPT	X		X	X
SCIM-II	X		X	X
tDCS	X			
Music Glove and FitMi arm training		1-10		
tDCS-Side Effects Questionnaire		1-10		
Pain and Fatigue		1-10		
Participant-tDCS &Arm Exercise Survey		1,6,10		
Participant- Usefulness of Intervention Survey			X	X
Caregiver tDCS&Arm Exercise Survey		1,6,10		
Caregiver-Usefulness of Intervention Survey			X	X

Post-treatment and Follow-Up Assessment (Duration: two-hours): During this period subjects will be asked to come within a-week after they have completed the study and at week 4 for follow-up. GRASSP, Grip Strength, SCIM-II and fNIRS measurements will be repeated at post-treatment visit and at 4-week follow-up visit.

7. Potential Risks/Discomforts

tDCS: Transcranial direct current stimulation (tDCS) is a technique that poses a non-significant risk to subjects. The safety of this technique has been addressed and tested by multiple researchers (e.g., Hummel, et al., (Hummel and Cohen, 2005); Fregni, et. al., (Fregni et al., 2006a, Iyer et al., 2005); Nitsche, et al., (Nitsche et al., 2003c, Nitsche et al., 2003b, Nitsche et al., 2003a), (Nitsche et al., 2004); Priori, et al., (Priori, 2003)). Researchers have concluded that tDCS, as applied in a manner similar to our proposed protocol, induces only temporary mood, cognitive / motor effects, and no negative side effects. No undesirable or long-lasting effects have been reported, nor have any subjects reportedly abandoned a study due to discomfort. The most common side effects according to a recent consensus are: headache, dizziness, nausea, itchy sensation as well as irritation under the area of the electrodes (Nitsche et al., 2008). Researchers at the National Institute of Neurological Disorders and Stroke (NINDS), Iyer et al., (2005) (Iyer et al., 2005) conducted a safety study on tDCS, investigating 20-minute sessions of 1 mA and 2 mA current stimulation with healthy controls (n=103). No negative effects were identified. Nitsche and colleagues (2004) found no measurable structural changes in brain tissue due to tDCS (Nitsche et al., 2004). Finally, two recent studies showed that

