Data for feasibility and adherence will be analyzed using descriptive statistics. For effectiveness, difference in GRASSP score in active arm and between active vs sham arm (immediately after treatment - baseline) will be analyzed with paired t test (if the normality is satisfactory with Kolmogrov-Smirnov test). If the K-S test suggests skewed distribution, we will conduct Wilcoxon signed rank test and Wilcoxon rank sum test for these two analyses.

In multivariable analysis, we will fit a mixed model for data collected at baseline and ten sessions and at 30-days follow-up in both study arms. Patient will be included as random effect of the mixed model. The fixed effects include treatment arm (active, sham) and time (0 for baseline, 1-10 for ten sessions). First, we will consider time levels as nominal and test interaction between treatment and time. The interaction will be added if it will be significant. Second, we hope to parametrically model time. The mean trajectory plot will guide us on the parametric form of time. Our emphasis will be linear time and 3rd-order polynomial time. We tend to favor the 3rd-order polynomial time as we believe that the GRASSP score will increase greatly for the first few sessions and then become stable.

In mixed model analysis, besides incorporating patient random effect, we will also test if there exists stronger correlation among measurements with shorter time intervals. We will specify a few serial correlation patterns including exponential, Toeplitz and banded Toeplitz. The random effect specification will be extended to incorporate random time slope. We will fit all these models and report AIC values to guide our decision on covariance pattern.

10. Potential Benefits

The results of these studies may benefit subsequent future subjects if remotely supervised, home-based combined tDCS and repetitive arm training proves to be effective when compared to repetitive arm training only.

The benefits of participating in this study may be improved arm and hand movement. However, there may be no benefit from participating in this study.

11. Risk-Benefit Ratio:

The potential improvement of arm and hand movement outweighs the risk of non-invasive brain stimulation, fatigue, pain and discomfort.

12. Consent Procedures:

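### The mixed model keeps arm-by-time only if it is significant; once dropped, the arm coefficient averages in the untreated baseline, and no other planned analysis compares the arms at 4 weeks

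*Combined protocol and SAP*

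**What the plan says.** Section 9 (Data analysis) plans two kinds of efficacy analysis for GRASSP.

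- **Simple comparison.** One part is within the active arm. The other is "between active vs sham arm (immediately after treatment - baseline"). The Wilcoxon fallback covers the same two comparisons. Neither uses the follow-up visit.
- **Mixed model.** The plan states: "we will fit a mixed model for data collected at baseline and ten sessions and at 30-days follow-up in both study arms". Baseline is therefore a row of the outcome, not a covariate: "The fixed effects include treatment arm (active, sham) and time (0 for baseline, 1-10 for ten sessions"). The random part starts from a patient effect ("Patient will be included as random effect of the mixed model"); a random slope and serial correlation patterns are to be compared by AIC. Time is first treated as nominal and arm-by-time is tested: "The interaction will be added if it will be significant". Time may then be modelled parametrically, and nothing says that the interaction returns at that step.

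No baseline covariate, baseline constraint or visit-specific contrast is named. The 4-week visit is nevertheless a planned assessment. Section 4 says: "Assessments will be repeated immediately after completion of 10 sessions and at 4-weeks follow-up". Section 6 says: "GRASSP, Grip Strength, SCIM-II and fNIRS measurements will be repeated at post-treatment visit and at 4-week follow-up visit". GRASSP prehension performance is the primary clinical outcome.

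**The concern.** No patient has been treated at time 0, and randomisation makes the expected arm difference there zero. An arm difference that is zero at baseline and non-zero later is, by definition, an arm-by-time interaction. The rule therefore removes the term that carries the treatment effect whenever that term misses significance, which is likely with 36 patients unless the effect is large or the within-patient correlation high.

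Two different quantities can result:

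- **Term dropped.** One arm coefficient stands for all time levels. It is diluted by baseline, carries any chance baseline imbalance, and cannot separate post-treatment from follow-up.
- **Term kept.** Visit-specific contrasts are available, but only in trials where the interaction happened to be large enough, so they tend to overstate the effect.

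The post-treatment comparison has its own test, which this rule does not touch. The 4-week between-arm comparison has nothing except the mixed model.

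**Working it through.** **Inputs from the documents.** Arms of 24 and 12 (Section 4). GRASSP at baseline, post-treatment and follow-up (Section 6, schedule of activities). Outcome levels and the interaction rule from Section 9. The documents give no SD, effect size, correlation, alpha or power, so there is no figure of the plan's own to reproduce.

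**Assumptions.** SD 1 at each visit, equal within-patient correlation rho, random intercept, complete data, two-sided 0.05 per test. Main case: effect 0.6 SD, rho 0.5/0.7/0.8, with 0.9 added as a sensitivity case. Results below follow that order of rho.

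**1. What the arm coefficient estimates when the term is dropped.** With arm + time and a random intercept, it is the unweighted mean of the arm differences over the time levels.

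- Three visits, sustained effect d: (0 + d + d)/3 = 0.67d, so 0.40 for d = 0.6.
- Three visits, effect at post-treatment only: (0 + d + 0)/3 = 0.33d, so 0.20, although the true 4-week effect is 0.
- Twelve levels as Section 9 is written (giving follow-up its own level, which the 0–10 coding does not do): 11/12 = 0.92d for an effect complete from session 1. For a linear rise to session 10 that then holds: (0.1 + 0.2 + … + 1.0 + 1)/12 = 6.5/12 = 0.54d.

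**2. How often the term is dropped (three visits).** The interaction F test has 2 and 68 degrees of freedom and noncentrality k × Σ(d_t − mean)²/(1 − rho), where k = 1/(1/24 + 1/12) = 8. For (0, 0.6, 0.6) the sum of squares is 0.16 + 0.04 + 0.04 = 0.24, so the noncentrality is 1.92/(1 − rho).

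| rho | Noncentrality | P(dropped), 0.6 SD | P(dropped), 0.4 SD | P(dropped), 0.8 SD |
|---|---|---|---|---|
| 0.5 | 3.84 | 0.62 | 0.81 | 0.37–0.38 |
| 0.7 | 6.40 | 0.41 | 0.70 | 0.15 |
| 0.8 | 9.60 | 0.22 | 0.58 | 0.04 |
| 0.9 | 19.20 | 0.02 | 0.27 | <0.01 |

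Under no effect it is dropped in about 95% of trials.

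**3. What is reported on each branch (simulation, 20,000 trials per setting, three visits).**

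- Dropped, sustained 0.6: arm coefficient averages 0.39–0.40.
- Dropped, post-only 0.6: arm coefficient averages about 0.20.
- Kept, sustained 0.6: 4-week change contrast averages 0.88/0.75/0.67, against a true 0.6. At rho 0.9 it is 0.61.

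**4. Chance baseline imbalance.** The standard error of the baseline difference is sqrt(1/24 + 1/12) = 0.354 SD. The arm coefficient moves with it at slope (1 + 2rho)/3 = 0.67/0.80/0.87. An imbalance of one standard error therefore shifts the coefficient by 0.24/0.28/0.31 SD. For comparison, an unadjusted change contrast moves the other way, at slope −(1 − rho): −0.18/−0.11/−0.07 SD.

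**5. False positives under no effect.** If either a significant interaction or a significant arm coefficient counts as positive, the rate is about 1 − 0.95² = 9.8% (simulated 9–10%). If a kept interaction must also show a significant post-minus-baseline contrast, it is 7.0–7.5% with three visits and 5.2–5.7% with twelve levels.

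**The case against.** The case on the other side is mainly about weight.

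- **The main comparison survives.** The post-minus-baseline test of the primary clinical outcome is not affected, feasibility is descriptive, and no 4-week hypothesis is stated. This stands, and it limits the point to the mixed model and the 4-week result.
- **The plan does not say which coefficient it will report.** It never states that the arm coefficient is the treatment effect once the interaction is gone. That is true, and the false-positive figures depend on decision rules supplied here. But the fixed effects left are arm and time, so any arm effect that model yields is the averaged one. The plan's silence is part of the problem.
- **The exact fractions are not properties of the plan.** An AIC-chosen covariance or parametric time would change the weights. Under exponential correlation (assumed days 0/14/42, 14-day correlation 0.7–0.9) baseline gets a weight of 0.39–0.46, not 1/3. Baseline stays in the average, and in that case dilution is worse.
- **Correlation may be high.** Patients are chronic and followed for a few weeks. At rho 0.9 the rule rarely bites for 0.6 SD (2%), though it does for 0.4 SD (27%). This limits how often the problem occurs, not its size when it does.
- **The 54% case is pessimistic.** Section 9 expects early improvement followed by a plateau. If the arm difference rises over two or three sessions, twelve levels recover 10.5/12 = 88% or 10/12 = 83%.
- **Baseline imbalance is ordinary sampling error.** It is in the coefficient's standard error, and an unadjusted change contrast carries it too, in the opposite direction. This is fair, and it is a reason to prefer a baseline-adjusted contrast.

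**Conclusion.** The concern holds and should be fixed. As written, Section 9 lets a p-value choose between two different estimands, and when the interaction is dropped the remaining arm coefficient includes a visit at which nobody had been treated. With the scheduled visits it recovers two thirds of a sustained effect and assigns a third of a post-only effect to a 4-week visit where there is none. The dilution follows from the model, with weights set by the covariance. How often it arises rests on assumed values: for 0.6 SD, from about 62% of trials at rho 0.5 down to about 2% at rho 0.9.

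Under no effect there is no bias, only a possible rise in the model's false-positive rate. No power or precision claim is made: at rho 0.5 the averaged coefficient has a smaller SD than the baseline-adjusted 4-week estimate (0.290 against 0.311). The immediate post-treatment comparison stands. The 4-week between-arm result cannot be interpreted without knowing which branch was taken.

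**What to change.** Replace the conditional rule in Section 9. Retain arm-by-visit whatever its p-value. From that model report the arm contrast with 95% CI at post-treatment and, as secondary, the same contrast at 4 weeks. Keep the visit-specific contrasts if time is later modelled parametrically.

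Name one contrast in advance. Either the difference in change from baseline or the baseline-adjusted difference would remove the dilution, but leaving both open brings back a choice. The baseline-adjusted form is preferable. At one visit, under the equal-correlation assumption, its variance relative to the change score is (1 − rho²)/(2(1 − rho)) = (1 + rho)/2, which is below 1 for any rho below 1, and it removes the imbalance shift in either direction. Also state how this model relates to the separate post-minus-baseline comparison.

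The follow-up needs its own time level, since the present coding stops at 10, and the levels should match the visits at which GRASSP is scheduled.

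Cost: a sentence or two in Section 9 and no new data. Always retaining the interaction costs two fixed-effect parameters with three visits, or 11 on the twelve-level reading.

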Brain motor cortex function: Functional near-infrared spectroscopy (fNIRS) device will be used to measure and record relative changes in oxygenated and deoxygenated hemoglobin from the motor cortex of the brain. This in turn will help examine and understand the effects of a combined tDCS/robotic assisted arm training treatment upon motor-related brain activity. FNIRS emits near-infrared light (740nm/850nm) into the head and acquires the amount of light returning using a detector positioned 3cm from the light source. It is a portable, non-invasive device similar to EEG and has been used in multiple research studies investigating brain function under various task-oriented settings. One major risk the fNIRS device poses is potential eye damage if the infrared light-emitting diodes (IR LEDs) are shined into an individual's eyes for an extended amount of time. This will be mitigated however by ensuring that the investigator leaves the device powered off before placing it on the user's head. An additional minor risk includes a mild discomfort caused by the tightness of the headband and straps. The investigator will adjust the device to provide optimal comfort to the subject. fNIRS will be performed at the baseline, immediately after completion of 10 sessions treatment and at 4-week follow-up.

5. Study Population:

36 adults with chronic incomplete cervical SCI will be recruited from TIRR/Memorial Hermann, local healthcare providers and from support groups in Houston area.

Participants will be included if they have:

- (1) diagnosis of a chronic incomplete cervical lesion as defined by the American Spinal Injury Association Impairment scale classification and at least for 6 months post injury;
- (2) upper-extremity weakness associated with tetraplegia with minimal residual thumb and index finger movement sufficient to grip small objects such as marble;
- (3) age 18 - 70 years;
- (4) no brain injury;
- (5) no planned alteration in upper-extremity therapy or medication for muscle tone during the course of the study;
- (6) no contradiction to tDCS
- (7) access to internet at home.

Subjects will be excluded if they have:

- (1) prior history of seizure;
- (2) modifications in chronic use of neuroactive medication (e.g., neurostimulants, anticonvulsants, or antidepressants) during study period (between baseline and follow-up);

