several sessions of tDCS are safe to be used in chronic pain syndromes such as fibromyalgia and spinal cord injury (Fregni et al., 2006c), (Fregni et al., 2006a). Thus, a growing body of research from different laboratories has shown that tDCS is a safe, noninvasive and painless technique for modulating neural excitability, with measurable but only transient effects.

The current protocol uses stimulation level of 2mA and a duration of 20minutes which falls within safety limits published by numerous clinical studies applying tDCS with human subjects. In our lab at Neurorecovery Research Center at TIRR, we completed several tDCS studies (HSC-MS-12-0868, HSC-MS-15-0269, HSC-MS-14-0354) and did not observe any serious side effects that required termination of subject's treatment program. As expected, tingling was the most common transient symptom followed by skin redness. Both are physiological responses to direct current stimulation and require no medical action.

The safety of tDCS in the pediatric and pregnant population has not been assessed. Therefore female subjects will be questioned for pregnancy at the screening, and pregnant women will be excluded. If a subject becomes pregnant during the course of the study, they will be withdrawn from the study.

Arm Exercise- Training: Patients with spinal cord injury sometimes develop pain or discomfort in the shoulders and arm. Subjects will be questioned for fatigue or discomfort during training sessions, and frequent breaks will be given to mitigate muscle fatigue. If any discomfort related to prolonged sitting happens, the training will be paused and participant will be encouraged to change his/her sitting position (weight shifting).

If there is evidence that pain or fatigue is worsened by the therapy, the sessions will be reduced or discontinued. All therapy sessions will be supervised and monitored by [name].

Assessment/Questionnaires: All assessments will be performed in a designated room inside NeuroRecovery Research Center at TIRR Memorial Hermann. None of these tests are either painful or uncomfortable to perform. In order to prevent potential embarrassment during the testing the test will be done individually and in private. If subjects feel uncomfortable in answering any of the questions they may stop the study at any time.

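### In the parametric step of the mixed model, the time form is guided by observed means with no rule, and the only named form that the three GRASSP visits can support, a straight line, biases the fitted post-treatment difference

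*Combined protocol and SAP*

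**What the plan says.** Section 9 (Data analysis) starts with simple tests on the change in GRASSP from baseline to immediately after treatment, within the active arm and between arms. These use no time form.

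The mixed model follows in two steps. In the first, time is nominal and the arm-by-time interaction is tested: "The interaction will be added if it will be significant". In the second, which is worded as a hope, time becomes parametric: "The mean trajectory plot will guide us on the parametric form of time. Our emphasis will be linear time and 3rd-order polynomial time". The cubic is favoured, for a stated reason: "we believe that the GRASSP score will increase greatly for the first few sessions and then become stable". AIC is named as a guide to the covariance pattern but not to the time form. Time is coded 0 at baseline and 1 to 10 for the sessions. A 30-day follow-up is to be in the model, but no time code is given for it.

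Section 4 (Study Design) sets a different data schedule for the clinical outcomes: "Assessments will be repeated immediately after completion of 10 sessions and at 4-weeks follow-up". The schedule of activities in section 6 agrees, marking GRASSP at baseline, post-treatment and follow-up and at none of the ten sessions.

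**The concern.** Two features of the parametric step combine.

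First, the time form is chosen after the outcome means have been seen. There is no criterion, no statement that the plot pools the arms, and no requirement that the choice precede unblinding.

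Second, the scheduled data support only one of the two emphasised forms. A cubic needs four coefficients per arm, and three visits supply three means. What remains is the straight line, which contradicts the plan's own expectation of an early rise followed by stability. A linear arm-by-time term forces the active-minus-sham difference at post-treatment to be a fixed fraction of the difference at follow-up. If the tDCS effect at the end of treatment is read from that fit, it can be well below the true value, and by how much depends on a follow-up code that section 9 does not state.

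**Working it through.** **Inputs from the document.** Section 5: "36 adults with chronic incomplete cervical SCI will be recruited". Section 4: "participants (n=24) in the experimental group" and "Participants (n=12) in the control group". GRASSP is taken at three visits (sections 4 and 6). The plan states no effect size, SD, power or significance level, so there is no figure of its own to reproduce.

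**Assumptions.** Two-sided 5% level, no dropout, a random intercept with independent within-person errors of variance σ², and a true active-minus-sham difference of 0 at baseline and δ at both later visits (the plateau case). Visit times are assumed. The schedule labels post-treatment day 5 and follow-up day 35, which puts them 30 days apart, but it gives no common clock from baseline.

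**Estimability.** Three distinct times give a polynomial design of rank 3. A cubic needs rank 4, so it cannot be fitted. A quadratic would be saturated and recover the post-treatment difference in full, but it is not one of the two emphasised forms. Visit windows would add distinct times only if actual days were used, and section 9 codes time by session.

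**Share of δ recovered by the linear form.** With balanced data the mixed-model slope equals the least-squares slope of the profile (0, δ, δ) on the visit times (t₁ = 0, t₂, t₃). With mean time m and S the sum of squared deviations from m:

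slope = δ[(t₂ − m) + (t₃ − m)]/S = δ·m/S, and the fitted change in the arm difference from baseline to post-treatment is t₂·m·δ/S.

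| Visit times | m | S | Share of δ at post-treatment |
|---|---|---|---|
| 0, 1, 2 (index) | 1 | 2 | 1 × 1/2 = 0.50 |
| 0, 20, 43 | 21 | 441 + 1 + 484 = 926 | 20 × 21/926 = 0.45 |
| 0, 20, 50 | 23.33 | 544.4 + 11.1 + 711.1 = 1266.7 | 20 × 23.33/1266.7 = 0.37 |
| 0, 15, 45 | 20 | 400 + 25 + 625 = 1050 | 15 × 20/1050 = 0.29 |
| 0, 10, 11 | 7 | 49 + 9 + 16 = 74 | 10 × 7/74 = 0.95 |

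Nominal time, or the change score, returns 1.00 in every row. In the first three rows the centred weight on the post-treatment visit is small (0; −1 against −21 and 22; −3.3 against −23.3 and 26.7), so the slope is essentially follow-up against baseline. With 0, 10, 11 the weights are −7, 3, 4, and this is not so.

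**Power on the same course.** Let δ be 1 SD of the change score, that is √2·σ. The slope has standard error factor σ/√S per person, so its standardised effect is √2·m/√S. The noncentrality is that value times √(24 × 12/36) = √8 = 2.83, on 34 df.

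- Post-treatment contrast: standardised effect 1.00, power about 78%.
- Slope, days 0, 20, 43: 1.414 × 21/30.43 = 0.976, about 77%.
- Slope, days 0, 20, 50: 1.414 × 23.33/35.59 = 0.927, about 72%.
- Slope, days 0, 15, 45: 1.414 × 20/32.40 = 0.873, about 67%.
- Slope, index 0, 1, 2: 1.414 × 1/1.414 = 1.00, the same as the contrast.

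The estimate at post-treatment is therefore distorted far more than the ability to detect a difference.

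**The case against.** The strongest reply is that the plan has largely covered itself. It prefers the cubic precisely because it expects a plateau, so it cannot be said to favour a line against its own expectation. The main between-arm comparison uses the change score, and the mixed model begins with nominal time; both recover the post-treatment effect in full. Section 9 never says that the tDCS effect will be read off a linear fit. If GRASSP were collected at all ten sessions and follow-up left out, a line would keep 0.64 to 0.96 of the effect for plausible rise shapes. All of this stands as a limit on the point. It does not remove it, because the favoured cubic cannot be fitted to the scheduled visits and session-level GRASSP is not scheduled.

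A reader might go further in three ways that the document does not support.

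- **That the effect would be lost.** If half the effect remained at 4 weeks, the line would return 0.16 to 0.25 of δ (index and day 0, 20, 43 to 50 coding), and −0.05 to 0 if none remained. But the phrase "with measurable but only transient effects" in section 7 is safety text about neural excitability. The only course forecast for GRASSP is a rise and then stability.
- **That the false-positive rate rises to about 9%.** That figure supposes that whichever of the slope and the post-treatment contrast is significant gets reported. For linear or saturated time on three visits the corresponding upper bound is 7.4%. The plan describes choosing by the shape of a plot, not by p-value, and does not say that the plot is drawn by arm.
- **That the trial's result is at stake.** The first aim is feasibility, and the simple effectiveness comparison does not depend on any time form.

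**Conclusion.** The point holds for the second, parametric step of the mixed model. The choice of form is data-driven and has no rule. Of the two named forms, only the linear one can be fitted to the three GRASSP visits, and it cannot represent the course that the plan expects. For an effect held to 4 weeks, the fitted post-treatment difference is about 0.37 to 0.50 of the true one under index coding or assumed days 0, 20, 43 to 50. It is about 0.29 under days 0, 15, 45, and about 0.95 under codes 0, 10, 11. The document does not settle which applies.

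Power falls from about 78% to between 72% and 77% under day coding 0, 20, 43 to 50, and to 67% in the least favourable coding examined. These figures assume an effect of 1 SD of change, a random intercept and no dropout. The recovered shares do not depend on the effect size, but a serial correlation pattern would change the weights somewhat.

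This is avoidable bias and discretion in a secondary model, worth correcting, and not a lost trial result.

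**What to change.** In section 9:

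1. State in advance that the mixed model for GRASSP uses nominal time at baseline, post-treatment and 4-week follow-up, with the arm-by-time interaction always included. This replaces the rule that keeps it only when significant.
2. Name the active-minus-sham change from baseline to post-treatment as the tDCS effect from this model, and report the 4-week contrast separately, each estimated freely.
3. Label any parametric curve exploratory, and choose its form from means pooled over both arms before unblinding.
4. Reconcile the 0 to 10 session coding with the GRASSP schedule in sections 4 and 6, and state how follow-up is coded if a curve is fitted.

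The cost is a few sentences and no extra data. If the effect truly grew in a straight line to 4 weeks, the free 4-week contrast would lose almost nothing: at days 0, 20, 43 its variance is 2.00σ² per person, against 43²/926 = 1.997σ² from the slope. The post-treatment contrast would give up precision that a line borrows (2.00σ² against 20²/926 = 0.43σ²), but that gain is valid only if the course is linear, which the plan does not expect.
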